3 PATIENT SELECTION

3.1 Inclusion Criteria

To be eligible for this trial, patients must meet all of the following eligibility criteria.

1. Patients with histologically confirmed locally advanced or metastatic endometrial carcinoma that is not amenable to curative surgical- or radiation-based intervention, who have received or declined at least one-line systemic chemotherapy.
2. Known microsatellite stable (MSS) and *FGFR1-4* aberration (activating mutations or amplification) as pre-identified in a Clinical Laboratory Improvement Amendments (CLIA)-certified laboratory
3. At least one measurable disease as defined by Response Evaluation Criteria in Solid Tumors (RECIST) 1.1.
4. Age ≥ 18 years.
5. Women of child-bearing potential (WOCBP) must have a negative serum pregnancy test prior to administration of the first dose of futibatinib within 7 days prior to initiation of therapy (C1D1), and must agree to use effective birth control initiated immediately following negative serum pregnancy test during screening period, during the study, and for at least 180 days after the last dose (or longer based on local requirements). Female patients are not considered to be of child-bearing potential if they are post-menopausal (no menses for 12 months without an alternative medical cause) or permanently sterile (hysterectomy, bilateral salpingectomy, or bilateral oophorectomy).
6. Adequate organ functions as defined below:
 - Absolute neutrophil count (ANC) $\geq 1,000 / \mu\text{L}$.
 - Hemoglobin (Hb) $\geq 9 \text{ g/dL}$.
 - Platelets $\geq 75,000 / \mu\text{L}$.
 - Total bilirubin $\leq 1.5 \times \text{ULN}$ (upper limit of normal); or total bilirubin $< 3 \times \text{ULN}$ with direct bilirubin $\leq \text{ULN}$ in patients with well documented Gilbert's Syndrome.
 - ALT $\leq 3 \times \text{ULN}$ or $\leq 5 \times \text{ULN}$ if liver metastases persist.
 - Serum phosphate $\leq 1.5 \times \text{ULN}$.
 - Serum calcium $\leq \text{ULN}$.
 - Serum albumin $\geq 3 \text{ g/dL}$.
 - Serum creatinine $\leq 1.5 \times \text{ULN}$ or calculated creatinine clearance (CrCl) $\geq 40 \text{ mL/min}$ by the Cockcroft-Gault method* or 24-hour urine collection.

*CrCl = $(140-\text{age}) \times (\text{weight [kg]}) \times 0.85 / (72 \times \text{serum creatinine mg/dL})$

7. Eastern Cooperative Oncology Group (ECOG) performance status of 0 to 1.
8. No prior combination treatment with anti-PD-(L)1 therapy and a FGFR inhibitor.

9. Ability to read and fully understand the requirements of the trial, willingness to comply with all trial visits and assessments, and willingness and ability to sign an institutional review board (IRB)-approved written informed consent document.
10. Any prior radiation must have been completed at least 14 days prior to the start of study drugs, and patients must have recovered from any acute adverse effects prior to the start of study treatment (Radiotherapy for extended field within 4 weeks or limited field radiotherapy within 2 weeks).
11. Ability to take oral medications without medical history of malabsorption or other chronic gastrointestinal disease, or other conditions that may hamper compliance and/or absorption of the study agents (feeding tube is not permitted).
12. Provision of an archival tissue block, or 10 formalin-fixed paraffin-embedded (FFPE) slides obtained within 6 months prior to study entry; or agreeing to have biopsies if archival tissues are not available.

3.2 Exclusion Criteria

Patients who meet any of the following criteria will be not eligible for the study:

1. Uncontrolled intercurrent illness including but not limited to ongoing or active infection requiring intravenous antibiotics, symptomatic congestive heart failure (New York Heart Association Class III or IV), history of myocardial infarction, unstable angina, stroke or transient ischemic attack within 6 months before study enrollment, history or current evidence of uncontrolled ventricular arrhythmia. Congenital long QT syndrome, or any known history of torsade de pointes, or family history of unexplained sudden death. Chronic diarrhea diseases considered to be clinically significant in the opinion of the Investigator. Other severe acute or chronic medical or psychiatric condition or laboratory abnormality that may increase the risk associated with study participation or futibatinib and pembrolizumab administration, or may interfere with the interpretation of study results, and in the judgment of the Investigator would make the patient inappropriate for entry into this study.
2. History and/or current evidence of any of the following disorders: Non-tumor related alteration of the calcium-phosphorus homeostasis that is considered clinically significant in the opinion of the Investigator; Ectopic mineralization/calcification, including but not limited to soft tissue, kidneys, intestine, or myocardia and lung, considered clinically significant in the opinion of the Investigator; and Retinal or corneal disorder confirmed by retinal/corneal examination and considered clinically significant in the opinion of the Investigator and a trained ophthalmologist who performs the test.
3. Having not recovered from a major surgical procedure or significant traumatic injury (i.e., still needing additional surgical or medical care for these issues): major surgical procedures \leq 28 days of treatment entry, or minor surgical procedures \leq 7 days. No waiting period required following port-a-cath or other central venous access placement.
4. Unresolved clinically significant Grade 2 toxicity from prior therapy.
5. Patient has an inability to swallow oral medications. Note: Patient may not have a percutaneous endoscopic gastrostomy (PEG) tube or be receiving total parenteral nutrition (TPN).
6. Clinically active bleeding, or active gastric or duodenal ulcer.
7. Fridericia's corrected QT interval ($QTcF = QT / \sqrt[3]{60/HR}$) $>$ 470 ms on ECG conducted during Screening. Patients with an atrioventricular pacemaker or other condition (for example, right bundle branch block) that renders the QT measurement invalid are an exception and the criterion does not apply.
8. History of allergic reactions to the study drugs, or any component of the products.

9. Currently receiving an investigational drug in a clinical trial or participating in any other type of medical research judged not to be scientifically or medically compatible with this study. If a patient is currently enrolled in a clinical trial involving non-approved use of a device, then agreement with the investigator and the sponsor is required to establish eligibility.
10. Any treatment specifically for systemic tumor control given within 3 weeks before the initiation of the study drugs, within 2 weeks if cytotoxic agents were given weekly, within 6 weeks for nitrosoureas or mitomycin C, within 5 half-lives for targeted agents with half-lives and pharmacodynamic effects lasting < 5 days, or failure to recover from toxic effects of any therapy before the initiation of the study drugs. A drug that has not received regulatory approval for any indication within 14 or 21 days of treatment for a non-myelosuppressive or myelosuppressive agent, respectively.
11. Has received a live vaccine within 30 days prior to the first dose of study drug. Examples of live vaccines include, but are not limited to, the following: Bacille Calmette-Guérin vaccine, measles, mumps, rubella, typhoid vaccine, varicella/zoster, and yellow fever. Seasonal influenza vaccines for injection are generally killed virus vaccines and are allowed; however, intranasal influenza vaccines are live attenuated vaccines and are not allowed.
12. Received strong inhibitors and inducers and sensitive substrates of CYP3A4 within 2 weeks, and avoid coadministration of strong inhibitors of CYP3A4 (see appendix A).
13. Symptomatic primary tumors or metastasis in the brain and/or central nervous system that are uncontrolled with antiepileptics and require steroids at a dose of prednisone > 10 mg/day or equivalent.
14. Evidence of leptomeningeal or lymphangitic carcinomatosis.
15. A history of another primary malignancy that is currently clinically significant, requiring active intervention except for hormone therapy.
16. Concurrent immunosuppressive therapy or steroid (> 10 mg/day prednisone or equivalent).
17. Previously documented or suspected autoimmune disease requiring active immunosuppressive therapy (adequately treated skin rash or replacement therapy for endocrinopathies is not excluded), and history of or current pneumonitis.
18. Lactation or pregnancy.
19. Known human immunodeficiency virus requiring HAART treatment due to unknown drug-drug interactions or known active hepatitis B or C virus infection.

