Patients are not permitted to receive any other investigational or any other anticancer therapy, including chemotherapy, immunotherapy, biological response modifiers, or antineoplastic endocrine therapy during the study treatment period.

Extended-field radiation therapy or palliative radiation to a focal site of measurable disease is also prohibited. If it is deemed in the best interest of the patient and after discussion between the Investigator and Medical Monitor, it can be administered, but the patient will be censored for the primary endpoint analysis.

Immunosuppressive therapy including steroids (> 10 mg/day prednisone or equivalent) is not permitted with pembrolizumab.

Concomitant strong inhibitors and inducers and sensitive substrates of CYP3A4 should be avoided, if possible, with futibatinib. Caution is advised if these drugs are given concomitantly (see [Appendix A: CYP3A4 and Transporters – Classification of Substrates, Inhibitors, and Inducers of CYP Enzymes and Transporters](#)). Alternative replacement is highly recommended.

Concomitant Medications and Therapies Requiring Precautions

Supportive treatment is allowed based on available institutional or local guidelines.

Local or regional palliative cryotherapy or radiation, such as for bone pain or palliative surgery (non-anti-neoplastic intent), are permitted (provided the target lesion is not a site of measurable disease and is not indicative of disease progression). Study therapy should be ceased a minimum of 2 days prior to administration of palliative treatment, and may be resumed 7 days after the procedure or when the patient has recovered from the side effects of the procedure.

The following medications/therapies may be given concomitantly under the following guidelines:

Hematologic Support: may be administered as medically indicated (that is, blood transfusions, granulocyte colony-stimulating factor, erythropoietin stimulating agents) according to the institutional site standards or American Society of Clinical Oncology (ASCO) guidelines ⁷⁶.[76].

Management of Diarrhea: Prophylactic treatment for diarrhea is permitted during the study if clinically indicated according to the institutional or published guidelines ⁷⁷.

Management of Nausea/Vomiting: Antiemetics may be administered as clinically indicated according to institutional standards or ASCO guidelines ⁷⁸.

Drug Interactions

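### Exclusion 13 requires both uncontrolled CNS disease and a steroid need above 10 mg/day, so it adds almost nothing to exclusion 16 and leaves some uncontrolled brain metastases to investigator judgment

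*Combined protocol and SAP*

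**What the plan says.** Section 3.2 opens with the rule that one criterion is enough to exclude: "Patients who meet any of the following criteria will be not eligible for the study". The criteria that bear on CNS disease are these.

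- **Exclusion 13** covers symptomatic primary or metastatic brain or CNS tumors that are "uncontrolled with antiepileptics and require steroids at a dose of prednisone > 10 mg/day or equivalent".
- **Exclusion 14** covers other forms of spread: "Evidence of leptomeningeal or lymphangitic carcinomatosis".
- **Exclusion 16** is a stand-alone steroid bar: "Concurrent immunosuppressive therapy or steroid (> 10 mg/day prednisone or equivalent".
- **Exclusion 1** opens with "Uncontrolled intercurrent illness including but not limited to ongoing or active infection requiring intravenous antibiotics". Its last sentence is a general clause on severe conditions that raise risk or cloud interpretation and that "in the judgment of the Investigator would make the patient inappropriate for entry into this study". CNS metastasis is not mentioned.
- **Exclusion 12** bars recent use of strong CYP3A4 inducers. Appendix A lists carbamazepine and phenytoin among them.

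Inclusion 7 (Section 3.1) requires "Eastern Cooperative Oncology Group (ECOG) performance status of 0 to 1". During treatment, Section 4.4 repeats the steroid threshold: "Immunosuppressive therapy including steroids (> 10 mg/day prednisone or equivalent) is not permitted with pembrolizumab".

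**The concern.** The lead-in to Section 3.2 works between criteria. It does not turn the 'and' inside exclusion 13 into 'or'. The steroid condition is largely covered by exclusion 16. What exclusion 13 alone could contribute is the control of the CNS disease, and the 'and' prevents that condition from excluding anyone by itself.

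Two things are at stake. The first is safety. If a patient with uncontrolled brain metastasis deteriorates and needs more than 10 mg/day of prednisone, Section 4.4 does not permit that dose with pembrolizumab. Adding carbamazepine or phenytoin would go against the advice in the same section to avoid strong CYP3A4 inducers with futibatinib. The second is attribution: neurological events from active brain disease can be hard to separate from drug effects, and safety is a co-primary objective (Section 1.1).

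**Working it through.** The plan gives no figure for this criterion, so the check is logical. Take a patient with symptomatic parenchymal CNS disease and define:

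- U = uncontrolled with antiepileptics
- R = requires prednisone above 10 mg/day
- T = actually takes more than 10 mg/day, for any reason

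Exclusion 13 as written is (U and R). Exclusion 16 is T. The alternative is (U or R).

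| U | R | T | Excl. 13 as written | Excl. 16 | Barred by 13 or 16 now | Barred with 'or' |
|---|---|---|---|---|---|---|
| 0 | 0 | 0 | no | no | no | no |
| 0 | 0 | 1 | no | yes | yes | yes |
| 0 | 1 | 0 | no | no | no | yes |
| 0 | 1 | 1 | no | yes | yes | yes |
| 1 | 0 | 0 | no | no | **no** | **yes** |
| 1 | 0 | 1 | no | yes | yes | yes |
| 1 | 1 | 0 | yes | no | yes | yes |
| 1 | 1 | 1 | yes | yes | yes | yes |

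Exclusion 13 applies to two of the eight combinations, and exclusion 16 already covers one of them. The only combination that exclusion 13 adds is U=1, R=1, T=0: uncontrolled, needing the higher dose, but not on it. The rows count logical cases. They say nothing about how often each occurs.

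The gap is U=1, R=0, T=0. The other criteria reach it as follows:

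1. Exclusion 14 does not reach parenchymal metastasis.
2. The opening clause of exclusion 1 turns on the word 'intercurrent', which can be read as separate from the study cancer. The last sentence does not use that word and can reach the case, but only through the investigator's judgment.
3. ECOG 0 to 1 is indirect. Attachment B defines grade 1 as symptomatic but ambulatory.
4. Exclusion 12 removes patients on carbamazepine or phenytoin, but not those on antiepileptics outside the CYP3A4 categories it names.
5. The screening CT listed in Section 5.1 covers chest, abdomen and pelvis. Brain imaging is not listed.

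On the design side, the two-stage rule in Section 7.1 (12 + 12 patients, at least 3 responses to continue, at least 7 for success) reproduces Table 11 by exact binomial calculation. At a 15% response rate, early stopping is 73.58% and the chance of success 4.87%; at 40% the chance of success is 86.20%. These depend only on the boundaries and the assumed response rates, so the wording of exclusion 13 does not alter them.

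**The case against.** The strongest reply is that the last sentence of exclusion 1 already handles the case. It lets the investigator exclude a patient for added risk or for interference with interpretation, which are the two harms at issue, and it has no carve-out for tumor-related conditions. Other exclusions also rest on the investigator's opinion. Exclusion 12, the ECOG limit and the radiation washout and recovery in inclusion 10 narrow the remaining group further. Much of this stands. A reader might infer that the protocol openly admits uncontrolled brain metastases; the documents do not support that. The narrower point remains: where a specific CNS criterion exists, a screener will naturally apply it, and here it does not exclude uncontrolled disease on that ground alone.

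A reader might also infer that the gap threatens the lead-in dose decision. The documents give little support for this. Under Section 5.6, DLTs must be related to study drug, and a death counts only if the cancer or an outside cause does not clearly explain it. In a patient with known uncontrolled brain metastasis, the cancer is the obvious explanation. Section 5.6 also allows replacement of a lead-in patient who has no treatment-related DLT and receives less than 75% of dosing because therapy is held for underlying medical issues. Any calculation that starts from one counted DLT would give the same result whatever caused that DLT, so it would say nothing about this criterion.

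Finally, how much CNS disease to allow is the sponsor's choice, and the documents do not state that 'or' was intended. That is fair, but a criterion that almost wholly repeats another does not express a clear choice.

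**Conclusion.** The point holds as a small drafting defect in a safety criterion. On its plain wording, exclusion 13 adds almost nothing to exclusion 16, and one clinically relevant group is left to discretion and indirect filters. The conclusion rests on reading 'and' as joining two required conditions, and on no other criterion naming parenchymal CNS disease. The size cannot be given: the documents state no frequency of brain metastases, and the group left after the other filters is probably small. The consequence is confined to patient safety and cleaner attribution of neurological events.

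**What to change.** In exclusion 13, replace 'and' with 'or'. Preferably reword it along these lines: *brain or other CNS tumor, primary or metastatic, that causes symptoms and is either uncontrolled (including despite antiepileptics) or needs more than 10 mg of prednisone daily or equivalent.* The first condition then no longer depends on seizure control alone, which the one-word change would leave unresolved for non-seizure symptoms.

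In the table, 'or' newly bars two combinations: uncontrolled disease needing 10 mg/day or less (U=1, R=0, T=0), and controlled disease needing more than 10 mg/day in a patient not taking it (U=0, R=1, T=0). The steroid limb would still largely repeat exclusion 16, which does no harm. The cost is a short amendment to Section 3.2 and possibly a few more exclusions. Section 7 needs no change.

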4 STUDY DESIGN AND TREATMENT PLAN

4.1 Study Design

This is an investigator-initiated NCCN (National Comprehensive Cancer Network)-supported phase II clinical trial (2020-IST-FUTI-000032) conducted at The University of Texas MD Anderson Cancer Center who will hold the Investigational New Drug (IND) for this study.

After patients with metastatic MSS endometrial carcinoma have signed the informed consent, patients will be enrolled to receive therapy for toxicity and efficacy evaluation.

The dose limiting toxicity (DLT) window is the initial 21 days of therapy.

- Enroll 6 lead-in patients to receive futibatinib 20 mg PO daily plus pembrolizumab 200 mg IV once every 3 weeks on day 1 of each cycle (dose level 1 in Table 1). If there is one or less DLT, the study will continue following a Bayesian optimal phase 2 (BOP2) design at dose level 1.
- If there are two or more DLTs, enroll another 6 lead-in patients to receive futibatinib 16 mg PO daily plus pembrolizumab 200 mg IV once every 3 weeks on day 1 of each cycle (dose level -1 in Table 1).
- If there are two or more DLTs at this dose level, the study will be terminated.
- If there is one or less DLT, the study will continue following a BOP2 design at dose level -1.
- The lead-in patients will be counted as the patients who are enrolled to stage I at the same dose level.

4.2 Treatment Plan

Table 3: Dose De-escalation for Futibatinib and Pembrolizumab

Dose Level	Futibatinib	Pembrolizumab
-1	16 mg PO daily	200 mg IV on Day 1
1	20 mg PO daily	200 mg IV on Day 1

As described in Section 2.4, the current clinical evidence supported the safety of futibatinib 20 mg PO daily in combination with pembrolizumab 200 mg IV once every 3 weeks in patients with advanced solid tumors.

One cycle of therapy is 21 days. As seen in [Table 3](#), futibatinib will be administered by mouth with or without food once a day and pembrolizumab will be given intravenously once every 21 days. Patients will be monitored for 60 minutes post pembrolizumab administration at C1D1, and then 30 to 60 minutes post infusion subsequently as clinically indicated. Appropriate dose modifications and interruptions for futibatinib, and interruptions for pembrolizumab without dose modification are allowed. No other investigational or commercially available agents specific for cancer control are permitted. Local palliation is allowed, but it is not allowed to the sole target lesion.

Investigational treatment with intravenous pembrolizumab 200 mg once every 3 weeks and oral futibatinib will be administered for up to 2 years as long as the patient is receiving benefit, tolerating the regimen, and does not meet any criteria for discontinuation of study treatment. At the discretion of treating physician, patients may receive intravenous pembrolizumab 400 mg once every 6 weeks subsequently.

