4.4 Dose Delays and Modifications

In addition to the following general guidelines for dose delays and modifications, the treating physicians as well as the study chair may institute additional remedies in the best interests of their patients according to their best medical knowledge.

The patients may interrupt treatment during study for palliative radiation or surgery, and may resume therapy when they recover, according to good medical practice.

If a patient experiences a clinically relevant toxicity which is known to be related to one drug in the regimen, then that drug may be modified according to the recommendation for that drug. Patient continuation on one single agent is allowed.

If a patient experiences a clinically relevant toxicity for which it is unclear which drug is the cause of the toxicity, then both agents may be modified according to the recommendation for each agent.

After a dose reduction for any toxicity, re-escalation is not permitted. For Grade 4 or recurrent G3 eye-related toxicities, the investigational treatment must be permanently discontinued.

Dose Delays and Modification Specific for Futibatinib

Description of Futibatinib – please see investigator's brochure (IB).

Futibatinib is a novel and selective small molecule irreversible, covalent inhibitor of fibroblast growth factor receptor (*FGFR*) 1–4.

Futibatinib will be supplied by Taiho Oncology, Inc. (Taiho). Detailed information, such as the requirements for accountability and disposal of study drug, can be found in the Pharmacy Manual, which will be provided separately.

Description of Study Drug

Futibatinib will be provided as 4-mg tablets for oral use. Please refer to the Investigator's Brochure for additional information.

Packaging and Labelling

Futibatinib will be packaged and labelled according to local laws and regulations.

Handling and Storage

Futibatinib tablets should be stored in accordance with the label.

Treatment Administration

Futibatinib is supplied as 4 mg tablets and will be taken orally at a dose of 20 mg daily until the patient meets any of the administration discontinuation or dose reduction criteria.

Futibatinib should be administered without or with food, with a glass of water.

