5.5 Guidelines for Evaluation of Tumor Markers and Tumor Responses

Evaluate tumor markers in those who have elevated tumor markers before treatment

Complete Response (CR): Tumor marker is below normal limit.
Partial Response (PR): More than 50% of tumor marker reduction.
Progressive Disease (PD): More than 25% of tumor marker increase.
Stable Disease (SD): Change not sufficiently defined as PR or PD.

Assessment of Tumor Response (RECIST version 1.1)⁸⁵:

The baseline imaging studies will be reviewed prior to the initial therapy. Tumor measurement and documentation will be performed after the first restaging workup.

Measurable Disease is defined by the presence of at least one measurable lesion.

Tumor lesions: Must be accurately measured in at least one dimension (longest diameter in the plane of measurement is to be recorded) with a minimum size of:

- 10mm by CT scan (CT scan slice thickness no greater than 5mm)
- 10mm caliper measurement by clinical exam (lesions which cannot be accurately measured with calipers should be recorded as non-measurable)
- 20mm by chest X-ray.

Malignant lymph nodes: To be considered pathologically enlarged and measurable, a lymph node must be ≥ 15 mm in short axis when assessed by CT scan (CT scan slice thickness recommended to be no greater than 5mm). At baseline and in follow-up, only the short axis will be measured and followed.

Non-measurable Disease

All other lesions, including small lesions (longest diameter < 10 mm or pathological lymph nodes with ≥ 10 to < 15 mm short axis) and truly non-measurable lesions. Lesions considered truly non-measurable include leptomeningeal disease, ascites, pleural/pericardial effusion, lymphangitic involvement of skin or lung, inflammatory breast disease, abdominal masses and abdominal organomegaly identified by exam that is not measurable by reproducible imaging techniques.

Target and Non-target Lesions

When more than one measurable lesion is present at baseline all lesions up to a maximum of five lesions total (and a maximum of two lesions per organ) representative of all involved organs should be identified as target lesions (this means in instances where patients have only one or two organ sites involved a maximum of two and four lesions respectively will be recorded).

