Lymph nodes merit special mention since they are normal anatomical structures, which may be visible by imaging even if not involved by tumor. Pathological nodes, which are defined as measurable and may be identified as target lesions, must meet the criterion of a short axis of ≥ 15 mm by CT scan. Only the short axis of these nodes will contribute to the sum. The short axis of the node is the diameter normally used by radiologists to judge if a node is involved by solid tumor. Nodal size is normally reported as two dimensions in the plane in

which the image is obtained (for CT scan this is almost always the axial plane; for MRI the plane of acquisition may be axial, sagittal or coronal). The smaller of these measures is the short axis. For example, an abdominal node which is reported as being 20mm x 30mm has a short axis of 20mm and qualifies as a malignant, measurable node. In this example, 20mm should be recorded as the node measurement. All other pathological nodes (those with short axis ≥ 10 mm but < 15 mm) will be considered non-target lesions. Nodes that have a short axis < 10 mm are considered non-pathological and will not be recorded or followed.

A sum of the diameters (longest for non-nodal lesions, short axis for nodal lesions) for all target lesions will be calculated and reported as the sum diameters. If lymph nodes are to be included in the sum, then as noted above, only the short axis is added into the sum. The sum diameters will be used as reference to further characterize any objective tumor regression in the measurable dimension of the disease.

All other lesions (or sites of disease) including pathological lymph nodes should be identified as non-target lesions. Measurements are not required and these lesions should be followed as 'present', 'absent', or in rare cases 'unequivocal progression'. In addition, it is possible to record multiple non-target lesions involving the same organ as a single item on the case record form (e.g., 'multiple enlarged pelvic lymph nodes' or 'multiple liver metastases').

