Partial Response (PR): At least a 30% decrease in the sum of diameters of target lesions, taking as reference the baseline sum diameters.

Progressive Disease (PD): At least a 20% increase in the sum of diameters of target lesions, taking as reference the smallest sum on study (this includes the baseline sum if that is the smallest on study). In addition to the relative increase of 20%, the sum must also demonstrate an absolute increase of at least 5mm. (Note: the appearance of one or more new lesions is also considered progression).

Stable Disease (SD): Neither sufficient decrease to qualify for PR nor sufficient increase to qualify for PD, taking as reference the smallest sum diameters while on study.

Response Criteria for Evaluation of Non-target Lesions ([Table 8](#))

Complete Response (CR): Disappearance of all non-target lesions and normalization of tumor marker level. All lymph nodes must be non-pathological in size (<10mm short axis).

Non-CR/Non-PD: Persistence of one or more non-target lesion(s) and/or maintenance of tumor marker level above the normal limits.

Progressive Disease (PD): Unequivocal progression of existing non-target lesions. (Note: the appearance of one or more new lesions is also considered progression).

Evaluation of Best Overall Response ([Table 9](#))

The best overall response is the best response recorded from the start of the study treatment until the end of treatment, taking into account any requirement for confirmation. The patient's best overall response assignment will depend on the findings of both target and non-target disease and will also take into consideration the appearance of new lesions.

Confirmatory Measurement

To be assigned a status of PR or CR, changes in tumor measurements must be confirmed by repeat assessments that should be performed ≥ 4 weeks after the criteria for response are first met. In the case of SD, follow-up measurements must have met the SD criteria at least once after study entry at a minimum interval of 8 weeks.

The duration of overall response is measured from the time measurement criteria are met for CR or PR (whichever is first recorded) until the first date that recurrent or PD is

objectively documented (taking as reference for progressive disease the smallest measurements recorded since the treatment started). The duration of overall CR is measured from the time measurement criteria are first met for CR until the first date that recurrent disease occurs.

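### Sections 4.2 and 4.4 disagree on local treatment of a target lesion, and no rule says how a locally treated target counts toward ORR, so a PR could reflect the local treatment.

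*Combined protocol and SAP*

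**What the plan says.** Four statements bear on which lesions may be treated locally.

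- Section 4.2: "Local palliation is allowed, but it is not allowed to the sole target lesion". The only limit is the sole target lesion.
- Section 4.4, opening guidelines: "The patients may interrupt treatment during study for palliative radiation or surgery, and may resume therapy when they recover". No lesion is excluded.
- Section 4.4, prohibited therapies: "Extended-field radiation therapy or palliative radiation to a focal site of measurable disease is also prohibited". An exception follows. After discussion between the investigator and the medical monitor, "it can be administered, but the patient will be censored for the primary endpoint analysis".
- Section 4.4, therapies requiring precautions: local cryotherapy, radiation or palliative surgery is permitted, "provided the target lesion is not a site of measurable disease and is not indicative of disease progression".

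On measurement, section 5.5 says that the diameters "for all target lesions will be calculated and reported as the sum diameters", with at most five target lesions and two per organ. PR is "At least a 30% decrease in the sum of diameters of target lesions, taking as reference the baseline sum diameters", confirmed by a repeat assessment at least 4 weeks later. No section says how a target lesion that has been irradiated, ablated or resected is measured or classified.

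On who is analysed, section 5.5 makes every dosed patient evaluable for efficacy. Section 7.1 defines the ITT population as all who received study agents. Section 7.2 puts eligible patients into the main response analysis, with a possible exception only for those never dosed.

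**The concern.** Target lesions are chosen from measurable lesions. For a patient with two or more targets, section 4.2 therefore allows what the later parts of 4.4 do not, and nothing says which text governs.

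The disagreement matters because local treatment acts directly on the quantity that defines response. If a treated target remains in the sum, its shrinkage or removal is credited to the study drugs. There is no control arm to reveal this, and for response the error runs only toward success. The success rule is 7 responses in 24 patients, so one or two misclassified patients can change the conclusion.

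The censoring clause does not settle the matter. It is attached to the prohibited radiation and not to surgery or cryotherapy. A binary response rate has no censoring, so the word could mean excluded, replaced or counted as a failure. Exclusion would contradict sections 5.5, 7.1 and 7.2.

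**Working it through.** **1. The plan's own figures.** Inputs from section 7.1: 12 patients in stage I, stop if fewer than 3 responses; 12 more in stage II; success at 7 or more of 24; p0 = 15%, p1 = 40%. With b(x; n, p) the binomial probability,

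P(success) = sum over x = 3 to 12 of b(x; 12, p) × P(Bin(12, p) ≥ 7 − x).

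This gives 4.87% at p = 0.15 and 86.20% at p = 0.40. All four rows of Table 11 reproduce.

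**2. When a treated target creates a PR.** Change = (follow-up sum − baseline sum) / baseline sum, with the treated lesion kept in the sum. PR needs −30% or lower. The lesion sizes are illustrative.

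| Targets at baseline | What happens | Change | PR? |
|---|---|---|---|
| 40 + 40 mm | one removed | (40 − 80)/80 = −50% | yes |
| 40 + 40 mm | one shrinks 60%, to 16 mm | (56 − 80)/80 = −30% | yes |
| 40 + 25 mm | 25 mm removed | (40 − 65)/65 = −38.5% | yes |
| 40 + 25 mm | 25 mm removed, other grows 10% | (44 − 65)/65 = −32.3% | yes |
| 3 × 30 mm | one removed | (60 − 90)/90 = −33.3% | yes |
| 3 × 30 mm | one removed, others grow 10% | (66 − 90)/90 = −26.7% | no |
| 5 × 20 mm | one removed | (80 − 100)/100 = −20% | no |

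With no response elsewhere, a false PR needs the treated lesion to be about 30% or more of the baseline sum, without enough growth elsewhere to offset its loss. The repeat scan at 4 weeks or later does not protect against this when the lesion has been removed, because it stays removed.

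**3. Effect on the decision rule.** The documents give no frequency of on-study local treatment, so both calculations below rest on assumptions.

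*(a) One patient certain to be called PR, all others responding at 15%.*

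- In stage I: sum over x = 2 to 11 of b(x; 11, 0.15) × P(Bin(12, 0.15) ≥ 6 − x) = 11.0%.
- In stage II: sum over x = 3 to 12 of b(x; 12, 0.15) × P(Bin(11, 0.15) ≥ 6 − x) = 9.3%.
- One in each stage: sum over x = 2 to 11 of b(x; 11, 0.15) × P(Bin(11, 0.15) ≥ 5 − x) = 20.1%.

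One such patient in stage I also lowers the chance of stopping early at a true 15% from 73.6% to 0.85^11 + 11 × 0.15 × 0.85^10 = 49.2%.

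*(b) A share f of true non-responders becomes a false PR, so that p = 0.15 + 0.85f.*

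| f | p | False-positive rate |
|---|---|---|
| 0 | 0.150 | 4.87% |
| 2% | 0.167 | 7.9% |
| 5% | 0.1925 | 14.2% |
| 10% | 0.235 | 28.8% |

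**4. If censored means dropped.** Suppose patients are dropped from stage II without replacement and the cut-offs stay the same. With 23 patients the type I error is 4.1% and power 84.2%; with 22 they are 3.4% and 81.5%. The wording of the clause therefore affects the design's properties too.

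**The case against.** The strongest reply is that a site must follow the whole protocol. The concomitant-therapy text in 4.4 is the specific text, so treating a measurable target breaches it whatever 4.2 says. This stands. A reader might infer that a site relying on 4.2 commits no deviation, or that local treatment of a target is simply permitted. The documents do not support that: they hold two conflicting rules, not a clear permission. The opening sentence of 4.4 adds little, since it concerns pausing and resuming treatment rather than which lesions may be treated.

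Second, where the censoring clause is applied, an irradiated patient would not simply be counted as a PR. This also stands, and it narrows the exposure. It leaves surgery and cryotherapy uncovered, and the clause itself undefined for ORR.

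Third, section 5.5 never states that a treated target stays in the sum. That is the literal reading of a rule covering all target lesions, in a text silent on treated ones. Table 7 returns not evaluable when targets are not all evaluated, and some assessors might classify a resected target that way. The text requires neither treatment of the lesion, which is why a rule is needed.

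Fourth, two equal 40 mm targets is a favourable example. It is, and the table shows cases with no PR. A false PR also needs no new lesion and no non-target progression.

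**Conclusion.** The inconsistency between 4.2 and 4.4 is certain from the text, and so is the absence of a rule for classifying a locally treated target. A confirmed false PR is possible on a literal reading of 5.5, but it is not automatic.

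The rates of 11.0%, 9.3% and 20.1% are conditional on one or two patients being certain to be called PR. A reader might take them as the trial's actual type I error; nothing in the documents supports that, because the frequency of local treatment is not given. Nor is this a sample-size error, since the stated operating characteristics are right. It is a gap in the definition of the primary endpoint. It should be closed because a single-arm trial with a cut-off of 7 in 24 is sensitive to one or two misclassified patients.

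**What to change.** 1. Reconcile section 4.2, the opening of 4.4 and the two later parts of 4.4 into one statement of which lesions may receive local treatment on study. Which clinical rule should stand is for the sponsor to settle.
2. In 5.5 and 7.2 state that, for ORR, a patient whose target lesion receives radiation, surgery or cryotherapy counts as a responder only if CR or PR was documented and confirmed before that treatment. Otherwise the patient counts as a non-responder and stays in the denominator.
3. Replace the censoring wording in 4.4 with this rule, so that it agrees with the analysis populations in 5.5, 7.1 and 7.2.
4. Leave the progression criteria in 5.5 as they are. Taking a treated lesion out of the progression assessment would need a new reference sum, which the plan does not define.

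The cost is wording only, with no added patients or procedures. The downside is that an occasional true responder treated locally before confirmation is counted as a non-responder, so the ORR may be slightly lower.
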